Official Title: Preliminary Studies to Test the Effects of Ambulatory Voice Biofeedback

NCT Number: 03416829

Date: June 16th, 2022

Study Protocol:

Study One will assess if AVB paradigms can effect short- and long-term changes in vocal loudness behavior in a small group of patients with vocal hyperfunction (VH). More specifically, it will determine which of three types of ambulatory feedback results in better learning/retention (100% frequency, 25% frequency, or delayed summary feedback every 2 minutes of voicing) of a new vocal behavior (reduced vocal loudness) in three groups of 15 patients with vocal fold nodules. It is hypothesized that patients receiving lower frequency or summary feedback will produce lower initial performance but higher short- and long-term retention than patients receiving feedback 100% of the time.

Inclusion/Exclusion criteria for the patients are summarized below:

Inclusion Criteria	Exclusion Criteria
Age: 18 – 65 years Previous monitoring: Patients must have successfully completed approximately 1 week of baseline voice monitoring in protocol 2011P002376 For Study 1 only: Diagnosis: vocal fold nodules	Non-English Speaker Unable to answer questions and/or follow instructions Patients with a sensitivity to hypoallergenic adhesive Pregnant women

Study One will include 54 total patients with phonotraumatic VH (45 patients + potential 20% dropout rate) and will be recruited from the Massachusetts General Hospital (MGH) Voice Center. The procedures and design for Study One are essentially identical to a previously approved IRB protocol (# 2014001870) which used normal subjects [37]. The proposed study seeks to replicate the previous results in patients with VH in order to move toward the clinical implementation of this approach. Each subject will be assigned (via block randomization) to three groups with different AVB schedules: 1) 100% immediate biofeedback (vibrotactile cueing every time the participant exceeds a vocal intensity threshold), 2) 25% immediate biofeedback (vibrotactile cueing every 4th time the participant exceeds a vocal intensity threshold), and 3) delayed summary biofeedback (no cueing; summary statistics shown every 2 minutes of voiced time). Patients with phonotraumatic VH have been chosen since reducing vocal loudness is often a goal of therapy.

All patients will be recruited following completion of Partners approved protocol 2011P002376. If a subject has not successfully completed monitoring during protocol 2011P002376, s/he will not be eligible for enrollment into this study. The patient's pre-therapy ambulatory monitoring from protocol 2011P002376 will provide a baseline for deriving each patient's vocal intensity biofeedback threshold. The overall design of the study will be three days: Two days of consecutive monitoring—a day of AVB (Day 1) and a subsequent day of ambulatory monitoring without AVB to assess if the desired vocal behavior is retained (Day 2). Seven days after Day 1, patients will wear the monitor again without AVB to assess any long-term retention of the desired vocal behavior (Day 3). As there is typically a 3-4 week waiting period for beginning voice therapy at the MGH Voice Center, it is reasonable to assume that patients will have the required number of weeks available for this protocol before therapy commences.

TABLE I. Study 1 time points and associated visits/procedures.

Time Point One (Day 1) Visit to MGH Voice Center	Time Point 2 (Day 2) Visit to MGH Voice Center	Time Point 3 (Day 3) Visit to MGH Voice Center

 1. Investigator places VHM, marks the subject's neck at location of sensor, programs VHM for subject's biofeedback, starts recording. 2. Investigator will teach subject how to use VHM and respond to biofeedback 	
 1. Investigator places VHM, marks subject's neck at location of sensor, programs VHM, starts recording 2. Investigator will review with subject how to use VHM 	
 1. Investigator places VHM, marks subject's neck at location of sensor, programs VHM, starts recording 2. Investigator will review with subject how to use VHM
Recording of voicing in daily life	Recording of voicing in daily life	Recording of voicing in daily life

 1. Subject will wear device and receive feedback on how loud s/he talks 2. Recording will automatically stop after 42 minutes of phonation (approx. 7-10 hours) 3. Subject will contact investigators to return device same day or charge device over night. 	
 1. Subject will wear device with no feedback 2. Recording will automatically stop after 42 minutes of phonation (approx. 7-10 hours) 3. Subject will contact investigators to return device same day or charge device over night. 	
 1. Subject will wear device with no feedback 2. Recording will automatically stop after 42 minutes of phonation (approx. 7-10 hours) 3. Subject will contact investigators to return device same day or charge device over night.

During biofeedback days, the VHM will only monitor the first 50,000 voiced frames—which are approximately 42 minutes of phonation (“frame” = 50 ms)—to ensure that each patient gets an equal opportunity to experience biofeedback. At typical phonation times of less than 10%, 42 minutes of phonation is achieved within 7-9 hours of monitoring time, which is an attainable goal for all patients.

The biofeedback threshold will be set at the 85th percentile of the patient's baseline (weeklong) vocal intensity histogram and the patients will be provided biofeedback to reduce the upper 15 % of their vocal intensity distribution (dB). More specifically, the VHM will provide a 250 ms vibrotactile cue via a smartwatch—see Figure 2(c)—every frame (100% frequency) or every 4th frame (25% frequency) the amplitude exceeds the biofeedback threshold. Those in the summary feedback group will receive a vibrotactile cue on their smartwatch after every 2 minutes of voiced time to alert them that their summary statistics are ready to be viewed. To ensure that the patient looks at the summary statistics in a timely manner and accurately understands their scores, multiple screens for user-interaction will be provided (they must indicate the correct score) and patient responses will be recorded in a text document.

The study endpoint will be achieved after satisfactory recording of 1 biofeedback day and two post-biofeedback days (3 total days).

Statistical Analysis Plan:

Study One will use a series of two 3 (Group) X 4 (Day - baseline, biofeedback, short- and long-term retention) mixed between/within ANOVAs will be conducted for the outcome variables Δ dB and overall percentage compliance. The findings of interest are the main effects of “Day” and the interaction effects of Group X Day. While appropriate post hoc tests will be conducted on the main effects (if significance is achieved), univariate follow-up tests, and if required, appropriate post hoc tests will be performed on the interaction effects. Results from our preliminary research [6] produced large effect sizes ($\eta^2 \approx 0.90$) between the biofeedback and non-biofeedback/baseline time periods. Furthermore, both limb and head/neck motor learning studies have demonstrated large effect sizes ($\eta^2 = 0.70-0.95$) between different feedback groups (decreasing frequency [10, 13-21, 49, 50] or delayed summary [10, 22-30, 51-53] feedback). Based on the

lower effect size ($\eta^2 = 0.70$) and the experimental design, power analysis indicated a sample of 14 participants per group with 80% power and alpha of 0.05. Since there are three experimental groups in Study One, the total sample size would need to be higher than 42 participants

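### Does the 25% feedback schedule need redefining because one sentence counts exceedances and another counts 50 ms frames?

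*Combined protocol and SAP*

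**What the plan says.** In the Study Protocol, the paragraph listing the three groups defines the 100% arm by "vibrotactile cueing every time the participant exceeds a vocal intensity threshold" and the 25% arm by "vibrotactile cueing every 4th time the participant exceeds a vocal intensity threshold". The delivery paragraph after Table I is more detailed. It says that "the VHM will provide a 250 ms vibrotactile cue via a smartwatch" at "every frame (100% frequency) or every 4th frame (25% frequency) the amplitude exceeds the biofeedback threshold". The paragraph before it sets the frame at 50 ms and says that on feedback days "the VHM will only monitor the first 50,000 voiced frames". The threshold is the 85th percentile of the patient's own baseline intensity.

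The hypothesis is that "patients receiving lower frequency or summary feedback will produce lower initial performance but higher short- and long-term retention", compared with feedback 100% of the time. The Statistical Analysis Plan tests it through "the interaction effects of Group X Day", with Δ dB and percentage compliance as outcomes. No cue count enters that analysis.

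No sentence says that a 'time' is a frame. Nor do the documents say what happens to a trigger that falls inside a running cue, or whether the count of four carries over from one loud run to the next.

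**The concern.** Feedback frequency is what separates these two arms, so its unit matters. A 'time' could mean a whole loud episode or a single 50 ms frame, and the two give different numbers of cues.

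The frame rule also sits awkwardly with the cue length. Triggers at every fourth adjacent frame are 200 ms apart, and each cue lasts 250 ms. In a sustained loud stretch a patient in the 25% arm might feel almost continuous vibration, much like a patient in the 100% arm. If so, the delivered contrast would be weaker than the labels suggest. A null 100%-versus-25% comparison could then reflect poor separation of the arms rather than absence of a learning effect. The summary arm is cued by voiced time, so its delivery is not affected.

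**Working it through.** **Inputs from the Study Protocol:** 50 ms frame, 250 ms cue, 50,000 voiced frames, 85th-percentile threshold (15% of frames above it at baseline behaviour). **Assumed, because the documents are silent:** length of loud runs, handling of a trigger during a cue, carry-over of the count.

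**1. The plan's own figure.** 50,000 × 0.050 s = 2,500 s, and 2,500 / 60 = 41.67 minutes. This agrees with the stated 42 minutes or so, so the frame length is sound.

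**2. Cue commands under the frame rule, count carried over.** 0.15 × 50,000 = 7,500 in the 100% arm; 7,500 / 4 = 1,875 in the 25% arm. The ratio is 0.25.

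**3. Cue commands if a 'time' is an episode.** With mean runs of m = 2, 4 or 10 frames there are 7,500 / m = 3,750, 1,875 or 750 episodes. A quarter of these is about 938, 469 or 188 cues. The absolute number changes with the unit, but the 25% arm still gets a quarter of the cues in the 100% arm.

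**4. Vibration time in one isolated run of k loud frames, count carried over.** If overlapping cues merge, the 100% arm vibrates for 50(k − 1) + 250 ms, and the 25% arm, with n cues in the run, for 200(n − 1) + 250 ms. If triggers during a cue are dropped, each accepted cue adds 250 ms. For k = 1 the 25% arm is averaged over the four positions of the count: 250 / 4 = 62.5 ms.

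| k | Merged, 25% / 100% arm (ms) | Ratio | Dropped, 25% / 100% arm (ms) | Ratio | Queued, ratio |
|---|---|---|---|---|---|
| 1 | 62.5 / 250 | 0.25 | 62.5 / 250 | 0.25 | 0.25 |
| 4 | 250 / 400 | 0.625 | 250 / 250 | 1.00 | 0.25 |
| 8 | 450 / 600 | 0.75 | 250 / 500 | 0.50 | 0.25 |
| 20 | 1,050 / 1,200 | 0.875 | 750 / 1,000 | 0.75 | 0.25 |

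**5. Whole day, count carried over.** A two-state Markov simulation used 50,000 frames, 15% of them loud, and 20 replicates. A mean run of 1.18 = 1 / 0.85 corresponds to independent frames.

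| Assumed mean run (frames) | Merged | Dropped | Queued |
|---|---|---|---|
| 1.18 | 0.34 | 0.40 | 0.25 |
| 2 | 0.45 | 0.51 | 0.25 |
| 4 | 0.61 | 0.59 | 0.25 |
| 8 | 0.75 | 0.62 | 0.25 |
| 16 | 0.85 | 0.62 | 0.25 |

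**6. Same rule, but the count restarts with each run.** Take isolated runs with geometric length, mean m = 2, so q = 1 − 1/2 = 0.5.

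- Share of runs cued: q³ = 0.125, or 12.5%.
- Triggers per run: q³ / (1 − q⁴) = 0.125 / 0.9375 = 0.133. Per loud frame this is 0.133 / 2 = 0.067, against a nominal 0.25.
- Merged vibration per run: 200 × 0.133 + 50 × 0.125 = 32.9 ms in the 25% arm, against 50 × 2 + 200 = 300 ms in the 100% arm. The ratio is 0.11.

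Here the 25% arm receives less than a quarter, and the contrast is wider than its label. At longer mean runs the merged ratio rises again, to 0.36 at m = 4 and 0.66 at m = 10.

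**The case for a change.** The strongest case for acting is that the manipulated variable should be defined without ambiguity in the document that describes it. The protocol caps monitoring at a fixed number of frames so that patients have equal exposure to feedback, so delivered exposure is its own concern. The overlap follows from its own figures: 200 ms is shorter than 250 ms. Even with no clustering of loud frames and continuous voicing, the ratio is 0.34 (merged) or 0.40 (dropped) if the count carries over. The earlier protocol on which the procedures are modelled may settle the matter, but a reader of this document cannot see it.

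Part of this stands. The two descriptions are not linked, and the handling of overlap is not written down. A reader wishing to replicate the schedule would have to ask.

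The rest does not carry. The delivery paragraph presents its rule as the more specific statement, although that phrase follows the threshold sentence rather than the group list. It attaches the labels 100% and 25% to how often cues are triggered, not to vibration time or to the share of loud episodes cued, and nothing else in the documents defines 25% in those other ways. That the arms are too close is one outcome among several, since step 6 gives the opposite. The step from vibration time to retention assumes that duration of vibration, rather than number of cues, drives learning. The documents do not support this, and no effect on Δ dB or compliance can be derived from them.

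**Conclusion.** This is a gap in descriptive detail, not a fault in the design or analysis. Read as the operational form of the group list, and with the count carried over, the frame rule delivers what its label says: 1,875 of 7,500 cue commands, or 25%, at baseline behaviour. Vibration time may differ from 25% in either direction. The illustrative values are 0.34 to 0.85 (merged, carried over, mean runs from 1.18 to 16 frames), 0.40 to 0.62 (dropped, same runs), 0.25 (queued), and 0.11 at a mean run of 2 frames (merged, count restarted). All rest on run lengths and device behaviour that the documents do not give, so they form a range and not a finding.

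Nothing in the analysis would change. The Group X Day comparison takes patients in the groups to which they were randomised and remains a valid comparison of the schedules as the device delivers them. What is affected is how a null result for one pairwise contrast would be read. A table of cues delivered on Day 1 could help there, but the documents do not confirm that cue times are logged. It would be descriptive only, and adjusting for it would condition on behaviour after randomisation. Bringing the two sentences to the same unit is a matter of wording. Which counting rule is meant is for the investigators to say.

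### The planned 3 × 4 mixed ANOVA conventionally drops any patient with a missing day, so the expected dropout could bias the Group × Day comparison; a likelihood-based model on Days 1–3 would use the data already collected

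*Combined protocol and SAP*

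**What the plan says.** The Study Protocol plans enrolment as follows: "Study One will include 54 total patients with phonotraumatic VH (45 patients + potential 20% dropout rate"). The target is stated as "in three groups of 15 patients with vocal fold nodules", with allocation by block randomisation. Below Table I, the protocol says when participation is complete: "The study endpoint will be achieved after satisfactory recording of 1 biofeedback day and two post-biofeedback days (3 total days"). It does not define a satisfactory recording.

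The Statistical Analysis Plan specifies "3 (Group) X 4 (Day - baseline, biofeedback, short- and long-term retention) mixed between/within ANOVAs" for two outcomes, Δ dB and overall percentage compliance. On the effects to be tested it says "The findings of interest are the main effects of “Day” and the interaction effects of Group X Day". It names no analysis population and no method for missing data, and it has no rule for a day that is missed or cut short.

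**The concern.** Over-enrolment protects the number of completers. It does not protect the randomised comparison. A conventional mixed between/within ANOVA needs a value in every Day cell, so a patient who returns Day 1 but misses Day 2 or Day 3 contributes nothing. With no other rule stated, the plan defaults to an analysis of completers.

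The trial asks which schedule gives better retention on Days 2 and 3. Baseline monitoring is an entry condition, so missing values can fall only on Days 1–3, the days that answer the question. If one arm lost more of its poor Day 1 responders than the others, its completers would look better on retention even if the schedules were equivalent.

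**Working it through.** **1. The plan's dropout figure.** 45 × (1 + 0.20) = 54, which reproduces the stated enrolment. This allows for 54 − 45 = 9 losses, or 3 per arm if allocation is 18/18/18 (equal allocation is assumed; the ratio is not stated). A true 20% loss from 54 would leave 54 × 0.80 = 43.2 completers, or 14.4 per arm. That is just above the 14 per group of the power statement and below 15.

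**2. Could loss differ by arm?** The arms differ in feedback only on Day 1. From the protocol's own figures, at baseline behaviour:
- 100% arm: 50,000 frames × 15% above threshold = 7,500 frames that could trigger a cue
- 25% arm: 7,500 / 4 = 1,875
- summary arm: 50,000 × 0.05 s = 2,500 s = 41.7 min; 41.7 / 2 = 20.8, so about 20 prompts

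The first two are upper bounds. A 250 ms cue spans five 50 ms frames, and behaviour is meant to change. Each summary prompt also opens several screens that need a correct answer. The figures show that the Day 1 experience differs. They do not show which arm would lose more patients.

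**3. Size of the completer bias.** Assumptions: 18 per arm, standardised outcomes, correlation ρ between Day 1 and Day 3, no true arm difference, one arm loses its k lowest Day 1 responders and the others lose none.

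Bias on Day 3 = ρ × (sum of the k lowest expected normal order statistics, sign reversed) / (18 − k).

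For n = 18 the three lowest are −1.820, −1.350 and −1.066, sum −4.236. With k = 3: 4.236 / 15 = 0.282.
- ρ = 0.5: 0.5 × 0.282 = 0.14 SD
- ρ = 0.7: 0.7 × 0.282 = 0.20 SD

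Simulation gave 0.13–0.20 SD. With k = 6, twice the planned allowance for one arm, the bias is 0.26–0.37 SD.

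**4. A different loss mechanism.** Loss falls on the poorest scorers of a variable correlated 0.3–0.8 with outcome, again with no true arm difference:

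| Loss by arm | Spurious difference, first arm minus third |
|---|---|
| 20/20/20% | about 0 SD |
| 30/20/10% | 0.08–0.19 SD |
| 40/10/10% | 0.12–0.32 SD |
| any split, loss unrelated to outcome | about 0 SD |

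**5. Does a mixed model remove it?** This depends on the model.
- Days 1–3, unstructured covariance, Day 1 observed for everyone: when Days 2 and 3 are missing together, the likelihood estimate of an arm's Day 3 mean is the completers' mean plus b × (Day 1 mean of all − Day 1 mean of completers), where b is the within-arm slope of Day 3 on Day 1. Under the deletions of step 3 the bias is about 0.00 SD.
- All four days with a single patient random effect, baseline constant: 0.06–0.20 SD remains, against 0.13–0.37 SD for completers under the same deletions (k = 3 and 6). A constant baseline says nothing about a patient's response and pulls down the estimated within-patient correlation.
- Day 1 also lost: no useful reduction (0.13–0.38 SD).

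The second case is relevant here. The threshold is each patient's own baseline 85th percentile, so if compliance means the share of frames at or below it, baseline compliance is about 85% for everyone. Δ dB is 0 at baseline if it is measured from baseline.

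**The case against.** Several stronger readings are tempting, and the documents do not support them.

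- **That a patient is analysed only with three satisfactory recordings.** The endpoint sentence reads as the point where participation is complete. Exclusion follows from the ANOVA, not from that sentence.
- **That patients will stop because of the feedback, probably unevenly by arm.** No dropout by arm and no intolerance is reported. Feedback lasts one day, Days 2 and 3 are the same in all arms, every patient has already completed about a week of monitoring, and the protocol regards 42 minutes of phonation as attainable by all. Only *could be uneven* is supportable.
- **That the cue counts show which arm suffers.** They are upper bounds, and they ignore the summary arm's screens.
- **That reasons for stopping are not collected.** No case-report form is shown, so silence does not settle this.

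A fair further objection is that the bias is small beside the planned effect. At η² = 0.70, f = √(0.70/0.30) = 1.53. If that is read as a between-group effect, the largest of three group differences is 1.53 × 3/√2 = 3.2 SD to 1.53 × √6 = 3.7 SD, so 0.14–0.20 SD is 4–6% of it. However, the stated "power analysis indicated a sample of 14 participants per group with 80% power and alpha of 0.05" was not reproduced from η² = 0.70, which gave 2–4 per group under the variants tried. In a one-way three-group comparison 14 per group matches f of about 0.50, a largest difference of 0.50 × 3/√2 = 1.06 to 0.50 × √6 = 1.22 SD. Against that, the bias is 0.14/1.22 = 11% to 0.20/1.06 = 19%.

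What stands of the objection is that the loss pattern is assumed, and that a mixed model helps only if it is specified correctly and Day 1 is observed.

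**Conclusion.** The point holds as a weakness in the choice of analysis. The plan expects loss, covers it only by recruiting more patients, and specifies an analysis that conventionally discards partly observed patients. The resulting Day 3 bias is conditional: about 0.14–0.20 SD if one arm of 18 loses its three worst Day 1 responders and the Day 1 to Day 3 correlation is 0.5–0.7, and about zero if loss is even across arms or unrelated to outcome. The correlation, the equal allocation and the link between loss and response are assumptions, and the direction of any imbalance is unknown. The change is worth making because it is cheap and needs no proof that the loss will be selective.

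**What to change.** - **Primary analysis:** for each outcome, a REML linear mixed model for Days 1–3 with Group, Day, Group × Day and an unstructured within-patient covariance (three variances and three covariances). Use every available day from all randomised patients with any post-baseline recording.
- **Baseline:** where an outcome is fixed at baseline by construction, leave baseline out of the repeated levels and test change from the fixed value (about 85% compliance, or 0 for Δ dB) as a contrast. Define both outcomes so that it is clear whether this applies.
- **Sensitivity analyses:** the three-day completer ANOVA, and an analysis restricted to full 50,000-frame recordings.
- **Reporting:** define a satisfactory recording, and report missed and shortened days by arm with reasons, which can be recorded when the device is returned.

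The cost is SAP wording and, if it does not already exist, one case-report field. No extra patients or visits are needed. There are three downsides. The model assumes data are missing at random given the observed days. It does not repair the loss of patients with no usable Day 1 recording. Shortened recordings are noisier and depart from the equal-exposure purpose of the frame cap, which is why the full-recording analysis is kept alongside.

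### Do the unstated sphericity correction, baseline score and retention contrasts undermine the 3 x 4 mixed ANOVA?

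*Combined protocol and SAP*

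**What the plan says.** The Statistical Analysis Plan applies "3 (Group) X 4 (Day - baseline, biofeedback, short- and long-term retention) mixed between/within ANOVAs" to two outcomes, Δ dB and percentage compliance. It says that "The findings of interest are the main effects of" Day and the Group x Day interaction. A significant interaction leads to "univariate follow-up tests, and if required, appropriate post hoc tests will be performed on the interaction effects". Neither outcome is defined, and sphericity is not mentioned.

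The Study Protocol section predicts that patients on reduced-frequency or summary feedback "will produce lower initial performance but higher short- and long-term retention" compared with the 100% group. On timing it says "The overall design of the study will be three days", so the fourth Day level, baseline, cannot come from this study's own recordings. It comes from earlier monitoring: the "pre-therapy ambulatory monitoring from protocol 2011P002376 will provide a baseline for deriving" each patient's threshold. On that threshold, "The biofeedback threshold will be set at the 85th percentile" of the patient's weeklong intensity histogram, and the cueing aims "to reduce the upper 15 % of their vocal intensity distribution".

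**The concern.** Three things look wrong.

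- **Retention.** Group x Day can be significant because of the feedback-day difference alone, a difference the sponsor itself predicts. That says nothing about retention. The retention claim then rests on follow-up tests chosen later, with no stated multiplicity rule.
- **Baseline.** If compliance is the share of voicing not above threshold, scored on the week that set the threshold, it is about 85% for every patient. If Δ dB is change from baseline, it is zero for every patient at baseline. Either way, one of the four Day levels has almost no variance.
- **Sphericity.** A level with almost no variance generally breaks sphericity, and uncorrected F tests can then reject too often.

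At stake would be the false-positive rate on the trial's main question, which feedback schedule is retained best.

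**Working it through.** The plan gives no error rate or variance for this point, so there is no figure of its own to reproduce.

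**Inputs from the documents.** 3 groups of 15, 4 Day levels, alpha 0.05, threshold at the 85th percentile.

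**Assumed inputs.** Normal data; common correlation ρ from 0 to 0.9; equal SDs on Days 1-3; baseline SD either 0 or equal to the day SD; 20,000 simulated trials per setting.

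**Degrees of freedom.** Day: 4 - 1 = 3. Group x Day: (3 - 1) x (4 - 1) = 6. Error: (45 - 3) x 3 = 126.

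**1. Can Group x Day be driven by Day 1 alone?** Yes. Let one group differ by d = 1 SD on Day 1 only, with ρ = 0.5. The noncentrality is n x (2/3)d² x (3/4)/(1 - ρ) = 15 x 0.667 x 0.75/0.5 = 15. With 6 and 126 df, power is 0.82. The first premise is correct.

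**2. What follows for retention?** Four comparisons matter: 100% versus 25% and 100% versus summary, on Days 2 and 3.

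If the analyst goes straight from Group x Day to four unadjusted tests, a ceiling for independent tests is 1 - 0.95⁴ = 18.5%. If a one-way test of groups on each day comes first, pairwise tests on a day with no group differences can be reached at most 5% of the time. For two independent days the ceiling is 1 - 0.95² = 9.75%.

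Simulated chance of at least one false retention finding per outcome, with a 1 SD difference on Day 1 only:

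| Follow-up route | Rate |
|---|---|
| Group x Day, then four unadjusted tests | 11.7-15.7% |
| Group x Day, per-day F, then unadjusted pairwise tests | 6.0-8.1% |
| Group x Day, then per-day Tukey | 5.0-7.1% |
| Four contrasts with Holm, no prior gate | 3.3-5.1% |

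**3. Would fixed Holm contrasts be a clear gain?** Take the predicted crossover: the 25% and summary groups 1 SD worse on Day 1 and 1 SD better on Days 2-3. Power per retention contrast is about 71% by the staged route and 64-66% with Holm. Holm therefore removes about 3 points of error (6.0 - 3.3 = 2.7; 8.1 - 5.1 = 3.0) and gives up 5 to 7 points of power (71 - 66 and 71 - 64).

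**4. How far does a constant baseline break sphericity?** With baseline variance 0 and unit variance on Days 1-3, the three orthonormal Day contrasts have variances 1 - ρ, 1 - ρ and (1 + 2ρ)/4. Epsilon is (sum)²/(3 x sum of squares).

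- ρ = 0: variances 1, 1, 0.25; ε = 5.0625/6.1875 = 0.818.
- ρ = 0.5: variances 0.5, 0.5, 0.5; ε = 1, so no violation.
- ρ = 0.9: variances 0.1, 0.1, 0.7; ε = 0.81/1.53 = 0.529.

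Under the null, uncorrected Group x Day rejects 4.9-9.2% over this range and comes near 9% only at ρ = 0.9. With a baseline as variable as the study days it rejects 4.7-5.0%. The uncorrected Day test rejects 4.9-8.2% and 4.5-5.1% respectively. A Greenhouse-Geisser correction gives 4.1-5.2% throughout.

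**The case for a change.** The strongest case for a change is that the protocol sets out to find which schedule is retained best, yet the text does not say which comparison answers that. The phrase on univariate follow-up could also mean testing Day within each group, which would not compare groups at retention. An analyst who skipped the per-day step could reach 12-16%, and a few sentences in the SAP would remove the doubt.

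A gated route can also lose power. If the groups differ at retention but not on Day 1, a corrected Group x Day test followed by per-day Tukey gives 42.5-62.3% per contrast (ρ 0 to 0.8), against 64.6-65.9% with ungated Holm. On sphericity, if the feedback-day SD were twice that of the retention days and baseline were constant, uncorrected Group x Day would reject 8.2-9.3% (ρ 0.3 to 0.7).

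Part of this stands: defining both outcomes and the baseline score, and naming the Day 2 and Day 3 comparisons, would make the report easier to read. The rest is weaker. The plan does name a univariate step before post hoc tests, and the high error figure ignores it. The predicted crossover is itself a Group x Day pattern, so the omnibus test is a sensible first step. No passage supports a doubled SD on the feedback day. The power comparison changes direction with the assumed pattern and the post hoc method, which is what a trade-off looks like.

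**Conclusion.** The omissions are real but minor, and the plan does not need to change. Followed in the order written, with univariate tests by day, the follow-up keeps the chance of a false retention finding at about 6-8% per outcome, or 5-7% with per-day Tukey. Holm contrasts would be stricter, but under the sponsor's own hypothesis they would be less powerful than the staged route.

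The sphericity effect is 0 to about 4 points above nominal. It depends on unstated scoring rules and an assumed correlation, and vanishes if baseline is scored so that it varies like the study days. Greenhouse-Geisser is a routine choice at analysis, and its absence would not alter the reading of a Day effect near the η² of 0.90 that the SAP expects.

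This conclusion assumes 15 per group with complete data, normal outcomes, equal SDs on Days 1-3, and a per-day reading of the univariate follow-up. If that step were dropped and no adjustment made, the error would rise to about 12-16%.

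### Baseline is a fourth level of Day and not a covariate, so retention-versus-baseline schedule comparisons fix the baseline slope at 1; adjusting for baseline dB is a nearly free precision gain of modest, uncertain size

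*Combined protocol and SAP*

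**What the plan says.** The Statistical Analysis Plan calls for "3 (Group) X 4 (Day - baseline, biofeedback, short- and long-term retention) mixed between/within ANOVAs", "conducted for the outcome variables Δ dB and overall percentage compliance". The findings of interest are the Day main effect and "the interaction effects of Group X Day". No covariate is named, and neither outcome is defined.

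The Study Protocol section settles where baseline comes from: "All patients will be recruited following completion of Partners approved protocol 2011P002376". That earlier monitoring "will provide a baseline for deriving each patient's vocal intensity biofeedback threshold". It covers about a week: "The biofeedback threshold will be set at the 85th percentile of the patient's baseline (weeklong) vocal intensity histogram". Patients are then assigned ("via block randomization) to three groups with different AVB schedules"), with 15 planned per group. The hypothesis is that the reduced-frequency and summary schedules do worse at first but are retained better.

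**The concern.** Baseline precedes randomisation, so any difference between the three groups at baseline is chance. Entering it as an outcome level gives each group its own baseline mean and counts that chance difference in Group X Day. A retention-day comparison read against baseline then subtracts the whole baseline difference, whatever the true relation between baseline and later loudness. If the true slope is below 1, this over-corrects for imbalance and carries baseline noise into the estimate. A covariate estimates the slope from the data.

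At stake is the precision of the randomised question, which schedule is better retained, in groups of 15. The baseline recording has already been made.

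**Working it through.** **Reference figure.** The plan gives no variance, baseline correlation or adjusted-analysis figure, so there is nothing of its own to reproduce on this point. Its sample-size calculation does not bear on the choice.

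**What the planned contrast is.** Let D0 be the difference between two groups in mean baseline dB, and D1, D2, D3 the differences on the study days. Group X Day contrasts have the form:
- Day 3 against baseline: D3 − 1 × D0. This is a change score with slope 1.
- Day 3 against Day 2, or either against Day 1: D3 − D2, and so on. D0 does not appear.

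If Δ dB means change from the patient's own baseline, its baseline level is 0 for everyone. Subtracting a patient's own constant leaves every within-patient contrast unchanged, so the same algebra holds.

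**Variance model (assumed).** Split the variance of one day's mean dB, scaled to 1, into a (stable patient level), b (patient-by-period drift between the baseline week and the study) and c (day to day), with a + b + c = 1. Take baseline as a mean over 7 days.
- Baseline variance V = a + b + c/7; true slope = a/V
- Change-score variance = 1 + V − 2a = 2b + c(1 + 1/7)
- Covariate-adjusted variance = 1 − a²/V
- Estimating the slope with N = 45 and 3 groups multiplies the adjusted variance on average by 1 + 1/(45 − 3 − 2) = 1.025 (normal covariate)

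Example, a = 0.5, b = 0, c = 0.5: V = 0.571, slope 0.875, change 0.571, adjusted 1 − 0.25/0.571 = 0.5625, ratio 0.984. After the factor 1.025 the ratio is 1.01.

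| a | b | c | slope | change | adjusted | ratio | ratio x 1.025 |
|---|---|---|---|---|---|---|---|
| 0.3 | 0 | 0.7 | 0.75 | 0.800 | 0.775 | 0.969 | 0.99 |
| 0.5 | 0 | 0.5 | 0.875 | 0.571 | 0.5625 | 0.984 | 1.01 |
| 0.7 | 0 | 0.3 | 0.94 | 0.343 | 0.340 | 0.993 | 1.02 |
| 0.9 | 0 | 0.1 | 0.98 | 0.1143 | 0.1141 | 0.998 | 1.02 |
| 0.5 | 0.1 | 0.4 | 0.76 | 0.657 | 0.620 | 0.943 | 0.97 |
| 0.5 | 0.3 | 0.2 | 0.60 | 0.829 | 0.698 | 0.843 | 0.86 |
| 0.3 | 0.3 | 0.4 | 0.46 | 1.057 | 0.863 | 0.816 | 0.84 |

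The asymptotic reduction is thus 0.2% to 3% without drift and about 6% to 18% with drift. Without drift, estimating the slope uses up the gain at this sample size.

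**Power.** Simulated three-group test on one retention day, 15 per group, arm means 0, −0.8 and −0.8 SD, 7-day baseline, change score against covariate:
- No drift: 68.1% and 68.2% (a = 0.3), 82.9% and 82.5% (a = 0.5), 97.4% and 96.9% (a = 0.7)
- Drift: about 76% to 78% (a = 0.5, b = 0.1), 66% to 74% (a = 0.5, b = 0.3), 55% to 63% (a = 0.3, b = 0.3)

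**Validity of the planned test.** Where baseline varies between patients with a common correlation of 0.3 to 0.9, the simulated null rejection of the 3 x 4 interaction was 0.04 to 0.06.

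**The case against.** The case for leaving the plan alone has several parts, and most of it stands.

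- **The gain may be nil.** The baseline is a week's recording. Without drift, the covariate gains nothing visible at 15 per group. Drift is plausible, because baseline belongs to a separate earlier protocol and the interval to Day 1 is not stated, but the documents do not quantify it. This stands, and it limits the size.
- **The hypothesised reversal does not involve baseline.** Lower initial performance with better retention is a contrast of Day 1 against Days 2 and 3, in which baseline cancels. This stands for that contrast. A comparison of retention relative to baseline remains affected.
- **Compliance may have no imbalance to adjust for.** If it means the share of voiced frames at or below the patient's own 85th percentile (an assumption), baseline compliance is about 85% for everyone. This stands: baseline compliance would be useless as a covariate, and the gain from baseline dB in that model is unknown.
- **Baseline as a Day level serves the Day question.** It does, and the fix keeps change from baseline for that purpose.

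Stronger readings are tempting. A reader might infer that chance imbalance biases the schedule comparison. Under randomisation it does so only conditionally on the imbalance observed, and the average is unbiased. A reader might also infer a large loss of power by treating baseline as one window comparable to a study day. The Study Protocol describes a weeklong baseline, so such figures do not apply.

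**Conclusion.** The point holds as a matter of precision. As written, group comparisons of a retention day against baseline use a fixed slope of 1, although the pre-randomisation dB value is available to estimate that slope. The benefit ranges from nothing visible (7-day baseline, no drift) to about 8 power points (strong assumed drift) for one retention day and a 0.8 SD effect. All variance shares, the drift and the effect size are assumptions.

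The power figures concern a single-day three-group test. They do not show that the covariate model beats the 3 x 4 interaction under every pattern of effects, nor that the planned test is invalid. Nothing is claimed for contrasts among Days 1 to 3, and little or an unknown amount for compliance. This is a free improvement, not a correction of an error.

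**What to change.** For the schedule comparisons, take baseline out of the Day factor. Use Days 1, 2 and 3 as outcomes with Group, Day, Group x Day, each patient's baseline mean dB and baseline dB x Day, allowing for repeated days within patient. Read the group differences on Days 2 and 3 from that model. Report change from baseline separately, as the answer to the Day question.

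Use baseline mean dB as the covariate in both models. Baseline Δ dB would be 0 for all if it is a change score, and baseline compliance may be almost constant. Define both outcomes in the same edit.

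The cost is SAP wording and no new data. Baseline plus its interaction with three days adds up to three parameters per model. A single-day comparison loses one error degree of freedom, from 45 − 3 = 42 to 41.
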